#### 4. TREATMENT PLAN

Adult subjects in the clinic who have one or more biopsy-proven cutaneous SCC or SCC-in situ (hereafter referred to as "SCC") lesions greater than or equal to 5 mm in diameter, at least one of which is being biopsied as a normal course of care, will be invited to participate in this trial. Eligibility of prospective participants will be confirmed, and subjects will enroll according to stated inclusion and exclusion criteria.

Screening visits may be combined with or without day 1 visit.

Prospective participants must be willing to sign a consent form. Subjects will also give consent to donate their SCC tissue for biomarker measurement and apply medication 3-times daily under bandage occlusion for 8 weeks. The anticipated bandage will be an adhesive bandage (e.g., "Band-Aid") with a non-adherent dressing, or paper tape with a non-adherent dressing.

Drug treatment: Subjects will be instructed to apply topical remetinostat to individual SCCs 3-times daily (TID) for 8 weeks. Patients will be asked to discontinue application of the medication at 8 weeks, approximately 2 weeks prior to their surgical excision(s), as dermal irritation from study drug may interfere with lesion identification at excision.

At least 1 target SCC will be identified requiring surgical excision per standard of care. In addition to being measured and photographed, this lesion(s) may be biopsied. Week 8 biopsy may be collected at the time of surgical excision of lesion(s). Histopathological evaluation of the specimen may be performed.

After an initial treatment application demonstration by the study team, treatment applications will be self-administered by the subject or a caregiver. Patients will receive oral and written administration instructions at the outset of the trial as follows:

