Given the absence of any remetinostat treatment related systemic AEs, together with the lack of effect on laboratory parameters or EKG, the minimal levels of remetinostat detected systemically reported in clinical studies to date, and the small BSA (< 0.5%) that will be treated with remetinostat gel, no lab assessments will be performed with the exception of a serum pregnancy test for women of child-bearing potential at baseline to assess eligibility for enrollment.

It is anticipated that the entire target tumor(s) will be surgically removed after the 8th week of treatment, in accordance with regular medical care; it is estimated that the surgical excision will occur between Weeks 10 to 14, depending on surgeon availability. A dose of remetinostat will be applied to the SCC by study personnel in clinic 30 mins before surgical excision. If surgical excision is delayed, i.e., does not occur at Week 10, remetinostat application may be continued for up to 4 additional weeks until surgical excision.

A follow-up visit will occur between Weeks 12 to 18 (approximately 2 to 4 weeks after Mohs/surgical excision), which may be in conjunction with surgery or a surgical follow-up visit,

or the visit may be conducted by phone. Patients may be contacted after completion of the study for additional follow up if deemed necessary by the Study Doctor.

SCC tissue biopsies will be collected from those who consent at baseline and Week 10 to evaluate the tumors treated with topical remetinostat gel 1%. The SCC biopsy will be collected in RNA later.

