The investigator has the right to discontinue a patient from study drug or withdraw a patient from the study at any time. In addition, patients have the right to voluntarily discontinue study drug or withdraw from the study at any time for any reason. Reasons for discontinuation of study drug or withdrawal from the study may include, but are not limited to, the following:

- Any subject who presents at screening or during treatment with a large (> 20 mm) SCC lesion: such a lesion will be discontinued from treatment (if applicable) and referred for evaluation for surgical resection. (If the patient has other, smaller lesions, these smaller lesions may be considered for enrollment in the study.)
- Subject withdrawal of consent at any time
- Any medical condition that the investigator or Sponsor determines may jeopardize the patient's safety if he or she continues in the study
- Investigator determines it is in the best interest of the patient
- Surgical or other treatment of target SCC before Week 8
- Pregnancy

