Thrombocytopenia CTC Grade ≥ 3 (platelet count ≤ 50 x  $10^9$ /L): Treatment must be discontinued for up to 4 weeks, by which time treatment must be permanently discontinued if the platelet count does not recover to ≥ 75 x  $10^9$ /L. On recovery of platelet count to ≥ 75 x  $10^9$ /L, treatment with remetinostat should initially be re-started BID every second day and then increased to BID daily application if tolerated. If event re-occurs, consider discontinuation of treatment.

**Diarrhea CTC Grade 1, an increase of < 4 stools per day over baseline; mild increase in ostomy output compared to baseline:** Reduce treatment frequency of remetinostat gel to every second day. Recommence BID daily treatment once diarrhea has resolved/returned to baseline status. If diarrhea does not recover after 4 weeks' every second day BID dosing, suspend treatment until diarrhea has resolved/returned to baseline status (maximum period of treatment suspension is 4 weeks).

Diarrhea CTC Grade ≥ 2, an increase of 4 to 6 stools per day over baseline; moderate increase in ostomy output compared to baseline; limiting instrumental activities of daily life (ADL): Treatment must be discontinued for up to 4 weeks, by which time treatment must be permanently discontinued if diarrhea does not resolve/recover to baseline status. Once diarrhea has recovered/returned to baseline status, treatment with remetinostat should initially be re-started BID every second day and then increased to BID daily application if tolerated. If event re-occurs, consider discontinuation of treatment.

If a patient lesion grows by 30% at the 4 week observation point, the patient would be directed to surgery instead of continued therapy on trial.

If 50% of total lesions being treated per protocol have grown, we would stop the study early.

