#### 10.1.1 Relevant Subset

All tumors with study drug application at 80% compliance and above will be included in analysis.

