#### 12.4.1 Analysis Population

We will first analyze the data by intention to treat analysis and then per-protocol analysis by only including tumors ≥ 80% compliant with drug treatment. Tumors with 79% or less compliant with

drug treatment will be reported as a deviation; tumors at least 80% compliant with drug treatment will not be recorded as a deviation. Patients will be instructed to use a band-aid or other form of occlusion. If the patient has difficulty with band-aid usage, the patient may stop and this will be documented.

For subjects who drop out, we will use data from their last study visit if they contribute a biopsy. The analysis population will include participants who have consented to undergo remetinostat treatment and who have at least 1 SCC tumor.

Safety analyses will include all subjects who received at least one dose of study treatment. Graded AEs (number and percent) will be summarized and reported according to the NCI CTCAE v5.0.

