#### 12.4.2 Analysis Plan

We will analyze the overall response rate of SCC based on the change in tumor area. Objective response rate (ORR) will be defined as the proportion of tumors with either a complete response or a partial response (PR) among all eligible and treated tumors. Toxicities will be graded according to the National Cancer Institute CTCAE v5.0. Exact binomial 90% confidence intervals (CIs) will be computed for the ORR. With a planned analysis on 30 per-protocol SCCs, this study would provide 91% power to reject an ORR of 15% if the true ORR is 40% or better, at one-sided alpha level of 0.05 with at least 9 responders.

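### No explicit rule says how a lesion sent to surgery for 30% growth at Week 4 counts in the per-protocol response rate, and one reading of the 80% compliance filter removes it because it grew

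*Combined protocol and SAP*

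**What the plan says.** **The stop.** Section 6.1, below Table 1, states: "If a patient lesion grows by 30% at the 4 week observation point, the patient would be directed to surgery instead of continued therapy". Section 4.2 lists among the reasons for discontinuation or withdrawal: "Surgical or other treatment of target SCC before Week 8". Section 6 takes off study any subject whose treatment has to be discontinued.

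**The analysis sets.** Section 10.1.1, under the primary outcome, states: "All tumors with study drug application at 80% compliance and above will be included in analysis". Section 12.4.1 states: "We will first analyze the data by intention to treat analysis and then per-protocol analysis", with the same 80% threshold for the second analysis. Neither section says what the 80% is a percentage of. Section 12.4.2 defines the ORR as "the proportion of tumors with either a complete response or a partial response (PR) among all eligible and treated tumors".

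**Early leavers.** Section 12.4.1 states: "For subjects who drop out, we will use data from their last study visit if they contribute a biopsy". Section 4 describes biopsies as depending on consent: "SCC tissue biopsies will be collected from those who consent at baseline and Week 10". It also allows the later biopsy to be taken at excision.

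**The success rule.** The synopsis and Sections 12.1, 12.4.2 and 12.6.2 give 91% power to reject 15% when the true ORR is 40%, at one-sided 5%, with at least 9 responders among 30 per-protocol lesions. The synopsis sets the sample size as 30 evaluable per-protocol tumors and leaves subjects without an evaluable tumor out of the count.

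**The concern.** A lesion that has grown by 30% after about four weeks of treatment is a treatment failure. Section 10.1 defines only complete and partial response, with no progression category, so nothing in the endpoint names this outcome. What happens to the lesion therefore depends on the rules for the analysis sets.

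On one reading of the compliance filter, the protocol's own stopping rule makes the lesion non-compliant. It then leaves the per-protocol set, and another lesion is treated to bring the set to 30. The set that carries the success rule would be selected on the outcome, and comparing its response rate with 15% would favor the drug. The intention-to-treat and per-protocol results could then point in different directions. Because the text does not choose between the readings, the choice could be made once the results are known.

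**Working it through.** **Inputs.** From the plan: 30 lesions, cut-off 9, null 15%, target 40%, one-sided 5%, exact 90% interval (Sections 12.4.2 and 12.6.2); three applications a day for 8 weeks (Section 4); Week 4 visit within one week either way (Section 9). Not in the plan: the share g of treated lesions stopped for growth. It is varied below.

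**1. The plan's own figure.** With X binomial, n = 30:
- P(X ≥ 9 | 0.40) = 0.906, which matches the stated 91%.
- P(X ≥ 9 | 0.15) = 0.0278. A cut-off of 8 gives 0.0698, so 9 is the smallest cut-off that holds 5%.

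**2. Compliance of a stopped lesion.**
- Planned applications: 3 × 56 = 168. Reaching 80% takes 0.8 × 56 = 44.8 days, or 6.4 weeks.
- Over 8 weeks, a stop at Week 3, 4 or 5 gives at most 3/8 = 37.5%, 4/8 = 50% or 5/8 = 62.5%. The lesion can never qualify.
- Over applications due up to the stop, it can reach 100% and stay in.

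**3. Error rate on the 8-week reading.** Assume a true ORR of 15% over all treated lesions, no responses among stopped lesions, independent lesions, and accrual continuing to 30 evaluable. The per-protocol rate is then 0.15/(1 − g).

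| g (assumed) | Per-protocol rate | P(X ≥ 9 of 30) |
|---|---|---|
| 0% | 15.0% | 2.8% |
| 5% | 15.8% | 3.7% |
| 10% | 16.7% | 5.1% |
| 20% | 18.75% | 9.4% |

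The probability equals 5% at a rate of 0.1663, so the limiting share is g = 1 − 0.15/0.1663 = 9.8%.

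**4. One data set, with stopped lesions restored as non-responders.** The p-value is one-sided against 15%; the limit is the exact 90% lower limit.

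| Responders/lesions | Lesions restored | Lower limit | p | 15% rejected? |
|---|---|---|---|---|
| 9/30 | 0 | 16.6% | 0.028 | yes |
| 9/33 | 3 | 15.03% | 0.0495 | yes |
| 9/34 | 4 | 14.6% | 0.059 | no |
| 10/38 | 8 | 15.03% | 0.0495 | yes |
| 10/39 | 9 | 14.6% | 0.058 | no |

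Four stopped lesions reverse the conclusion at 9/30 (4/34 = 12% of treated lesions). At 10/30 it takes nine (9/39 = 23%).

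**5. Power if stopped lesions are kept as non-responders among the 30.** If 40% refers to all treated lesions, power stays at 0.906. If it refers only to lesions not stopped, then at g = 10% the overall rate is 0.40 × 0.9 = 0.36, and P(X ≥ 9 | 0.36) = 0.808.

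**The case against.** The strongest reply is that the plan already handles the lesion. The ORR runs over all eligible and treated tumors, and the intention-to-treat analysis comes first. A treated lesion that grew has neither a complete nor a partial response, so it counts against the drug. This stands for the intention-to-treat result. A reader might infer that the plan has no rule at all, or that the lesion disappears from every analysis, and the documents do not support that. The reply does not reach the per-protocol set, where the success rule is stated. The last-visit rule does not override the 80% filter either. It depends on a biopsy, and it is unclear whether tissue from an early excision would meet that condition or whether a patient sent to surgery is a dropout.

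A second reply is that counting compliance to the directed stop is the more natural reading. Section 12.4.1 reports tumors below 80% as deviations, so the 8-week denominator would record a patient who followed Section 6.1 as a protocol deviation. This is a fair argument, but the text does not settle the matter.

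Three further points stand in part:
- Replacement is inferred from accrual to 30 evaluable tumors. No lesion-replacement rule is written.
- The inflation assumes that the 15% null refers to all treated lesions. If it refers to the per-protocol set, there is none.
- Section 6.1 directs the patient, not the lesion, to surgery. In a patient with several lesions, a shrinking one could also leave the set and pull the other way.

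Section 12.7 also limits the stakes, since a reduction in tumor size would lead to a proposed randomized trial.

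**Conclusion.** The point holds as a gap in the per-protocol definition. No explicit, unconditional rule covers a lesion stopped for Week 4 growth. Under the 8-week denominator the stated 80% filter removes it because of its outcome; under a denominator that ends at the directed stop it stays in and there is no bias.

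On the adverse reading the size depends on g. The error rate rises from 2.8% to 3.7% at g = 5%, 5.1% at 10% and 9.4% at 20%, and it passes the planned 5% only above about 9.8%. These figures rest on the assumptions listed with the error-rate table, including a 15% null over all treated lesions.

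A reader might conclude that the per-protocol ORR is certain to be biased upward. The undefined denominator and the unknown g do not support that. A reader might also conclude that four stopped lesions would overturn any positive result. That is true only at exactly 9/30; one more responder raises the number to nine. The matter should be corrected before analysis, but it does not invalidate the design.

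**What to change.** In Section 12.4.1, state that a lesion sent to surgery for growth at Week 4:
- counts as a non-responder in both the intention-to-treat and the per-protocol ORR, and is one of the 30;
- has its compliance computed over the applications due up to the protocol-directed stop;
- contributes its last measurement whether or not a biopsy is obtained.

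This is a change of wording. Section 9 already schedules tumor measurements at Week 4 and at early termination, so no visit is added. With these lesions kept among the 30, the error rate stays at 2.8% for a 15% ORR over all treated lesions.

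The cost is that the per-protocol ORR may be lower. Power remains 91% if the 40% target was meant for all treated lesions. If it was meant only for lesions not stopped, power is 81% at g = 10%.

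The fix does not require the 30% growth trigger to be defined as area. An area trigger corresponds to about 14% growth in each diameter (√1.30 = 1.14), so if diameter was intended it could send more lesions to surgery. The sponsor should choose that metric.

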# **PROTOCOL SYNOPSIS**

TITLE	A Phase 2 Open-label, Single-arm Trial of the Efficacy and Safety of Topical Remetinostat Gel as Neoadjuvant Therapy in Patients with Squamous Cell Carcinoma Undergoing Surgical Resection				
STUDY PHASE	Phase 2				
INDICATION	Treatment of squamous cell carcinoma (SCC) and squamous cell carcinoma in situ (SCC-IS)				
INVESTIGATIONAL PRODUCT	Topical remetinostat gel 1%				
PRIMARY OBJECTIVE	To determine if topical remetinostat gel treatment 3-times-daily (TID) for 8 weeks will decrease SCC tumor area (in mm²) by at least 30%				
	To determine the overall response rate (ORR) of SCC tumors to 8 weeks of TID treatment with topical remetinostat gel				
SECONDARY OBJECTIVE	To assess the safety and tolerability of remetinostat gel 1% when applied topically TID under occlusion for 8 weeks as follows:				
	
 
Incidence, type, and severity of adverse events (AEs)
 
Incidence and nature of serious adverse events (SAEs)
 
				
	Incidence of AEs leading to remetinostat discontinuation or interruption				
	
 
Adherence to the treatment, measured by number of patients discontinuing the treatment (for any reason) and treatment interruptions
 
				
TREATMENT SUMMARY	Apply topical remetinostat gel 1% 3 times daily (TID) under bandage occlusion for 8 weeks				
STUDY POPULATION	Adults of either gender with squamous cell carcinoma (SCC) lesions ≥ 5 mm. See Section 3.1 for detailed eligibility.				
SAMPLE SIZE	30 SCC per-protocol evaluable tumors. The maximum number of subjects contributing evaluable tumors will be 40, but can be less to obtain the 30 SCC per-protocol evaluable tumors. Participating subjects that do not contribute evaluable tumors will not be counted towards this total. It is anticipated that no more than 40 subjects will participate overall.				

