# 9. STUDY CALENDAR

	Pre-treatment Day -2 to -30	Pre-treatment Day -1	Treatment Day 1	Treatment Week 4 (+/- 1 week)	Week 10 Visit* (+ 4 weeks)	Follow-up Week 12-18*	Early termination	
Remetinostat treatment			x	x	x			
Informed consent	Х							
Medical history	Х							
Concurrent meds	X							
Physical exam	Х	Х		Х	Х		Х	
Vital signs	Х	Х		Х	Х		Х	
Height	Х							
Weight	Х	Х		Х	Х		Х	
ECOG score	Х			Х	Х		Х	
Serum pregnancy test	Х							
Adverse event evaluation			X					
Tumor measurements and photographs		х		Х	x		x	
Tumor Biopsy		Х				(X)		
Patient Calls			X					

\*Week 10 visit may occur between weeks 10-14, depending on surgeon availability. Study drug will be applied for 8 weeks in total; if surgical excision is delayed, the study drug may be applied for up to 4 additional weeks (for a total of up to 12 weeks)

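### The plan does not say whether the per-protocol or the all-treated response rate decides success, and lesions stopped for early growth may drop out of the per-protocol set

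*Combined protocol and SAP*

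**What the plan says.** **Decision rule.** The synopsis and Sections 12.1, 12.4.2 and 12.6.2 give the same rule: 30 per-protocol SCCs, null ORR 15%, alternative 40%, one-sided alpha 0.05, at least 9 responders, 91% power. No responder count is given for any other number of tumors.

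**Analysis set.** Section 10.1.1, under the primary outcome, says "All tumors with study drug application at 80% compliance and above will be included in analysis". Sections 12.1 and 12.4.2 instead take ORR over all eligible and treated tumors, with an exact 90% CI. Section 12.4.1 lists intention to treat first and the 80%-compliant analysis second. It uses a dropout's last visit only if a biopsy was contributed.

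**Recruitment.** The synopsis says "The maximum number of subjects contributing evaluable tumors will be 40, but can be less to obtain the 30 SCC per-protocol evaluable tumors", and then "Participating subjects that do not contribute evaluable tumors will not be counted towards this total".

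**Treatment and growth rules.** Section 4 says "Subjects will be instructed to apply topical remetinostat to individual SCCs 3-times daily (TID) for 8 weeks". Section 6.1 says "If a patient lesion grows by 30% at the 4 week observation point, the patient would be directed to surgery instead of continued therapy". The Study Calendar allows one week either side of the week-4 visit. Section 4.2 says of a lesion found to exceed 20 mm that "such a lesion will be discontinued from treatment (if applicable) and referred for evaluation for surgical resection". Section 6 takes subjects who discontinue off study. The plan does not say what compliance is a percentage of, or how a lesion stopped for growth is classified.

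**The concern.** There are two linked gaps.

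The first holds under any reading of compliance. The only stated success count belongs to one set, while the definition of ORR and the first-listed analysis belong to another. In an open-label, single-arm trial that choice should be fixed before the responses are known.

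The second depends on how compliance is counted. Measured against the prescribed 8 weeks, a lesion sent to surgery at week 4 cannot reach 80%, so it leaves the per-protocol set because it grew. The per-protocol ORR then omits some of the least favorable outcomes. If recruitment continues until 30 compliant tumors are reached, the omitted lesions are in effect replaced, and the 9-of-30 rule may no longer hold its nominal error.

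**Working it through.** **Inputs.** From the documents: n = 30, cut-off 9, 15% versus 40%, one-sided 0.05, 80% compliance, 8-week course, week-4 visit at 3 to 5 weeks. Not in the documents, so assumed: the share g of treated lesions stopped for growth, and the rate q at which those lesions would otherwise have responded. Tumors are treated as independent, as the plan does.

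**1. The plan's figure.** With X binomial, P(X ≥ 9 | 30, 0.40) = 0.906, which agrees with the stated 91%. P(X ≥ 9 | 30, 0.15) = 0.0278. A cut-off of 8 would give 0.0698, so 9 is the smallest valid count.

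**2. Exposure at a week-4 stop.** 3/8 = 37.5% and 5/8 = 62.5%. The 80% mark is 0.8 × 56 = 44.8 days. On the full-course reading, every lesion stopped at this visit is excluded.

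**3. Can the two analyses disagree?** Suppose four non-responding lesions are removed and replaced. The exact (Clopper-Pearson) 90% intervals are:
- per-protocol 9/30 = 30.0%: 16.6% to 46.5%, which rejects 15%;
- all treated 9/34 = 26.5%: 14.6% to 41.6%, which does not.

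Reusing a cut-off of 9 for all treated tumors gives an error of 0.0587 at N = 34 and 0.1354 at N = 40.

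**4. Error of the 9-of-30 rule with replacement.** Hold the all-treated ORR at 15%. With m lesions removed and replaced, g = m/(30 + m), and the response rate among those kept is (0.15 − qg)/(1 − g).

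| q | m removed | Rate among those kept | P(X ≥ 9 of 30) |
|---|---|---|---|
| – | 0 | 15.0% | 0.0278 |
| 0% | 3 of 33 | 16.5% | 0.0478 |
| 0% | 4 of 34 | 17.0% | 0.0563 |
| 0% | 10 of 40 | 20.0% | 0.1287 |
| 5% | 4 of 34 | 16.3% | 0.0452 |
| 5% | 5 of 35 | 16.7% | 0.0506 |

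The error reaches 0.05 at g = 9.8% if q = 0, at 14.0% if q = 5%, and at 24.6% if q = 10%.

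**5. Without replacement.** With 30 treated, 4 removed and q = 0, the rate is 0.15 × 30/26 = 17.3%, and P(X ≥ 9 | 26, 0.173) = 0.0258. That is below 0.0278, so there is no inflation.

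**6. Cut-offs for the all-treated set.** The smallest count with error at or below 0.05 against 15%:

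| N | Cut-off | Error across the range | Power at 40% |
|---|---|---|---|
| 30–33 | 9 | 0.0278 to 0.0495 | 0.906 to 0.956 |
| 34–38 | 10 | 0.0240 to 0.0495 | 0.927 to 0.973 |
| 39–40 | 11 | 0.0250 to 0.0299 | 0.955 to 0.965 |

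At each N from 30 to 40 this is also the smallest count whose exact 90% lower limit exceeds 15%.

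**7. Power if 40% applies to compliant tumors only.** With q = 0 and 10% stopped, the all-treated ORR is 0.40 × 0.90 = 36%, and power at 9/30 is 0.808. With 20% stopped it is 32%, and power is 0.659.

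**The case against.** **The text may keep these lesions in.** Section 12.4.1 reports tumors below 80% as deviations, which sits badly with a stop that the protocol itself orders. Section 6.1 also says "If 50% of total lesions being treated per protocol have grown, we would stop the study early", so a growing lesion can be regarded as treated per protocol. If compliance runs to the stop date, the lesion stays in as a non-responder and the bias does not arise. This stands: the text is unsettled, and neither reading can be ruled out.

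**The all-treated set is already testable.** With a 15% null and one-sided 0.05, an exact 90% lower limit above 15% is the test. This also stands. A reader might infer that the set has no test at all, and that is too strong. What is missing is a statement that this criterion decides success, and how it ranks against the repeated 9-of-30 rule.

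**Error inflation needs several conditions together:** the full-course denominator, replacement (implied by the synopsis but not stated), enough removals, and little chance that a removed lesion would have responded. Section 6.1 does not say whether 30% growth means diameter or area, and Section 4 notes that drug irritation may interfere with identifying the lesion, so some stopped lesions might have responded later. All of this stands.

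**Disagreement is confined to a narrow margin.** In the four-lesion example the two analyses differ only at exactly 9 responders, which has probability 3.4% when the all-treated ORR is 15%. With three removed (N = 33, cut-off 9) they never differ. That limits the size of the problem but does not settle which result governs.

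**Conclusion.** The point holds as a gap in the decision rule, with a conditional bias attached. Under any reading of compliance, the plan does not say whether the per-protocol or the all-treated result decides, and the two can fall on opposite sides of 15%.

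If compliance is measured against the 8-week course, lesions stopped for week-4 growth leave the per-protocol set because of their outcome, and that ORR is biased upward. The same applies to a lesion stopped for exceeding 20 mm before about day 45, although the only scheduled on-treatment measurement is at week 4.

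A reader might infer that the trial's type I error is in fact above 0.05. The documents do not support that. It would require replacement and about 10% or more of treated lesions removed if none could respond, or about 14% or more at a 5% response rate. The removal rate is unknown, and below those levels the slack between 0.0278 and 0.05 absorbs the effect. The matter is worth fixing because it is cheap and the plan already computes the less biased analysis. Confidence is medium.

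**What to change.** Leave the clinical stopping rules unchanged.

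- **12.4.2:** State that ORR over all eligible and treated tumors decides success, and that success means an exact 90% lower limit above 15%: 9 responders for N = 30–33, 10 for 34–38, 11 for 39–40.
- **10.1.1 and 12.4.1:** State that a lesion that itself meets the week-4 growth rule or the on-treatment 20 mm rule stays in the analysis as a non-responder, whatever its doses taken or biopsy status. A sibling lesion stopped only because another lesion grew is classified by its own last measurement.
- Keep the 80%-compliant analysis as supportive.

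**Cost.** A few sentences and no new data, because week-4 and early-termination measurements are already scheduled. The reported ORR may be lower. Power is at least 90.6% for N = 30 to 40 if the all-treated ORR is 40%. If 40% applies to compliant tumors only, power at 9/30 falls to about 81% with 10% of lesions stopped for growth and about 66% with 20%, assuming that none of those could respond. At N = 33 and N = 38 the error is 0.0495 under independence, so there is little room for correlation between lesions of one patient.

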## 11.2 Data and Safety Monitoring Plan

The Stanford Cancer Institute Data and Safety Monitoring Committee (DSMC) will be the monitoring entity for this study. The DSMC will audit study-related activities to determine whether the study has been conducted in accordance with the protocol, local standard operating procedures, FDA regulations, and Good Clinical Practice (GCP). This may include review of the following types of documents participating in the study: regulatory binders, case report forms, eligibility checklists, and source documents. In addition, the DSMC will regularly review serious adverse events and protocol deviations associated with the research to ensure the protection of

human subjects. Results of the DSMC audit will be communicated to the IRB and the appropriate regulatory authorities at the time of continuing review, or in an expedited fashion, as needed.

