#### 12.6 Sample Size

#### 12.6.1 Overall Accrual estimates

Subjects will be enrolled from Stanford Dermatology (Adult) clinic which sees approximately 4,000 dermatology patients per month (or 48,000 visits per year). Approximately 20% of these patients have current or past skin cancer. Enrollment of SCC subjects for Stanford clinical trials has been rapid. 30 per-protocol SCC lesions are anticipated to be evaluated within the first 12 months. We will only advertise and enroll from Stanford Dermatology clinic. It is anticipated that at least 10 subjects will consent to baseline and post-treatment biopsies.

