# 12.6.2 Sample size justification

For primary objective analysis, with a planned analysis on 30 per-protocol SCCs, this study would provide 91% power to reject an ORR of 15% if the true ORR is 40% or better, at one-sided alpha level of 0.05 with at least 9 responders.

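### Does the 50% lesion-growth stop in Section 6.1, which Section 12 never mentions, undermine the 91% power?

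*Combined protocol and SAP*

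**What the plan says.** Section 6.1 ends with two growth rules, one after the other. The first concerns one patient and gives a margin and a visit: "If a patient lesion grows by 30% at the 4 week observation point", the patient goes to surgery. The second concerns the whole study: "If 50% of total lesions being treated per protocol have grown, we would stop the study early". It gives no visit, no minimum number of lesions and no growth margin.

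Section 12.2 plans no interim analyses, and the rest of Section 12 does not mention the growth stop. Section 12.6.2 says that "this study would provide 91% power to reject an ORR of 15% if the true ORR is 40% or better", based on 30 per-protocol lesions, a one-sided 0.05 level and at least 9 responders. The same figure appears in the Synopsis and in Sections 12.1 and 12.4.2.

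Other sections bear on how the stop would be read:
- Section 12.4.1 has a "per-protocol analysis by only including tumors ≥ 80% compliant with drug treatment".
- Section 12.4.2 takes the response rate "among all eligible and treated tumors".
- Section 11.2 makes the DSMC the monitoring body and says that "the DSMC will regularly review serious adverse events and protocol deviations associated with the research".

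**The concern.** The rule can end the study on a proportion of accumulating tumor measurements, which are also the raw material of the primary endpoint. The denominator could be the planned 30, the lesions assessed so far, the lesions started so far, or the compliant tumors of Section 12.4.1. Compliance over the full course is not known while a lesion is still on treatment. Growth could mean any increase, or the 30% of the preceding sentence could carry over. Two people following the text could therefore stop at different points.

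A stop that can end the trial without success also lowers the chance of success. If the loss were large, 91% would overstate what the design delivers. The study is open-label and Section 10.1.5 has a physician measure size at the visit, so an undefined trigger leaves discretion over when the study ends.

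**Working it through.** **1. The plan's own figure.** Inputs from Section 12.6.2: n = 30, null 15%, alternative 40%, success at 9 or more responders.

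- Power: P(X ≥ 9 | 30, 0.40) = 1 − Σ(x = 0 to 8) C(30,x) 0.4^x 0.6^(30−x) = 0.906.
- Type I error: P(X ≥ 9 | 30, 0.15) = 0.028. With 8 it would be 0.070, so 9 is the smallest valid cut-off.

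The 91% is the exact one-stage power, with no early stop in it.

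**2. Adding the rule.** Each lesion independently responds (0.40), grows (g) or does neither (0.60 − g). An exact recursion tracks responders and grown lesions up to 30. A stopped study counts as not successful, and growers never respond and are not replaced. The documents give no value for g, so a range is assumed. The schedules of checks are also assumed.

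| Reading of the rule | g = 10% | 20% | 30% | 40% |
|---|---|---|---|---|
| 15 of the planned 30 have grown | 0.906 | 0.906 | 0.901 | 0.820 |
| Half of those assessed so far, each lesion from the 10th | 0.905 | 0.876 | 0.750 | 0.488 |
| Same, but more than half needed | 0.906 | 0.896 | 0.824 | 0.607 |
| Half of those assessed so far, each lesion from the 15th | 0.906 | 0.901 | 0.837 | 0.605 |
| Half, one check at the 15th lesion | 0.906 | 0.903 | 0.871 | 0.742 |

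**3. How much growth is needed.** If 40% of lesions respond, at most 60% can grow. For half of all lesions to grow, 0.50/0.60 = 83% of the non-responders must grow. At g = 30% half of them do (0.30/0.60). At the null rate of 15% the corresponding share is 0.50/0.85 = 59%. The rule therefore bites mainly where the drug is failing.

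**4. Type I error.** With response 15%, the second reading gives 0.028, 0.027, 0.026 and 0.021 at g = 10, 20, 30 and 40%. No reading in the table exceeds 0.028, because stopping only removes paths to success.

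**5. Caliper noise as a rough anchor for g.** Assume an unchanged lesion, area as the product of two diameters, caliper error SD 0.5 to 1 mm, and rounding to whole millimeters. Across the eligible range of 5 to 20 mm, noise alone counts 34 to 44% of such lesions as grown if any increase counts, and 0 to 25% with a 30% area margin. If all 60% of non-responders are unchanged, g is 0.60 × 34% to 0.60 × 44%, or about 20 to 26%. With the margin it is 0 to 15% (0.60 × 25%). The noise figures rest on an assumed SD and ignore true growth.

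**6. What the documents supply for the rest.**
- Visit: Sections 9 and 10.1.4 limit scheduled on-study measurement to week 4 and the end-of-treatment visit.
- Unit: Sections 1.1, 10.1, 12.1 and 12.4 all express size change as area.
- Oversight: Section 11.2 names the DSMC as monitor and lets it review case report forms and source documents.
- Analysis after a stop: Section 12.4.2 gives a proportion with an exact 90% interval, which can be computed at any number of lesions. A lower limit above 15% is the same test as 9 of 30 at one-sided 0.05, so only the count of 9 is tied to 30.

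**The case for a change.** The best case for a change is that the adjacent patient-level rule has a margin and a visit, while the study-level rule has neither. Even a harm stop needs a denominator and a first point of application. If the rule runs on lesions assessed to date from the 10th and 30% of lesions grow, power falls from 0.906 to 0.750, about 16 points. A few words in Section 6.1 and a cross-reference in Section 12 would cost no patients.

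The looseness of the sentence stands. The denominator, the minimum count and the growth margin are not written down, and Section 12 should not be read as having accounted for the rule.

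The rest is weaker. The 16 points need both a 30% growth rate and a check after every lesion from the 10th, and neither is in the documents. The rule sits under stopping criteria, beside the send-to-surgery rule, and tests no hypothesis, so Section 12.2 is not contradicted. Power for an efficacy test is commonly quoted without a harm stop. Restating it here would replace one clear conditional figure with a range built on guessed inputs. Any definition would also be the sponsor's own choice; nothing in the documents points to a better rule.

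**Conclusion.** No change to the plan is called for. This is missing detail in a harm-based stop, of a kind that the investigator and the DSMC can settle sensibly if the situation arises. It is not an error in the design or in the 91%. The stated power reproduces exactly (0.906) as the fixed-sample figure, type I error cannot rise above 0.028, and the planned interval still serves if the study ends early.

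The effect on power is not determined by the documents. At growth rates of 10 to 30% it is practically nil when 15 of the planned 30 must grow (0.906 to 0.901), and ranges from nil to about 16 points under a running count from the 10th lesion (0.905 to 0.750). At 40% growth, where two thirds of the non-responders have grown (0.40/0.60), every reading loses power. These figures assume independent lesions, a true response rate of 40%, no replacement of growers, and a stopped study counted as unsuccessful. A reader should take 91% as the power given that the study runs to 30 evaluable lesions.
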